7.2.4 Safety follow-up

Safety follow-ups will be performed 90 ± 7 days after the last dose (refer to [Table 14](#)).

Table 14. Procedures of the safety follow-ups

Period	Safety Follow-Up	Note
Day	28 Days (± 7 Days)	
Vital Signs	X	Vital signs include body temperature, pulse, respiratory rate, and blood pressure. See Section 8.2.4 of the protocol for detailed requirements
Body Weight	X	
Physical Examination	X	See Section 8.2.2 of the protocol
ECOG PS	X	
Laboratory tests		
12-Lead ECG	X	Refer to Section 8.2.3 of the protocol for details
Hematology/Clinical Chemistry/Urinalysis/Routine Stool	X	See Section 8.2.1 of the protocol
Coagulation Function	X	
Thyroid Function	X	
Immunogenicity (ADA, Nab)	X	

Period	Safety Follow-Up	Note
Day	28 Days (\pm 7 Days)	
AE Assessment	X	All AEs from the time of signing the ICF to the end of safety follow-up or the start of new anti-tumor therapy (whichever occurs first) and all SAEs from signing of ICF to the end of safety follow-up will be recorded in the CRF
Concomitant Medications	X	Drugs related to the treatment of AEs other than solvents within 28 days before the first dose of the study drug until 30 days after and 30 to 60 days after the end of the treatment should be documented
End of treatment visit		
Survival Status	X	
Subsequent Anti-Tumor Treatment	X	
Response Evaluation		
Imaging Assessment	X	If the treatment is discontinued for reasons other than radiologically confirmed PD, imaging evaluations shall be performed as much as possible per the scheduled time points until any of the following events occurs: start of new anti-tumor therapy, PD, withdrawal of ICF, or death.

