16. Pulmonary function test: Maximum vital capacity, the forced expiratory flow at 25-75% of forced vital capacity (FEF25-75), the peak expiratory flow rate (PEF), the maximum expiratory volume per second, diffusing capacity of the lungs for carbon monoxide (DLCO) and oxygen saturation, which will be performed during the screening period and based on clinical indicators as determined by the investigator thereafter. Arterial blood gas test: optional. This test includes partial arterial pressure of oxygen (PaO₂), partial arterial pressure of carbon dioxide (PaCO₂), arterial oxygen saturation (SaO₂), and pH, and can be performed during the screening period. Pulmonary function test and arterial blood gas test indicators will be based on the actual conditions at each site.
17. Immunogenicity blood samples will be collected once within 0.5 h before SHR-1210 infusion on D1 of cycle 1, cycle 2, and the third cycle of every three cycles thereafter (cycles 5, 8, 11, etc.), once at the end of the treatment, and once per month at safety follow-ups after withdrawal for 3 times (if applicable). In case of national holidays, the blood collection time may be adjusted as appropriate. If the subject develops SHR-1210 infusion-related reactions, blood samples should be collected as close as possible to the onset of the event, to the end of the event, and about 30 days after the end of the event, for immunogenicity comparison and analysis. Immunogenicity blood samples should be collected following the study protocol. However, if deemed necessary by the investigator, unscheduled immunogenicity blood samples may be collected. Tests will be performed at the central laboratory. Four (4) mL of blood will be collected each time for immunogenicity.
18. The safety assessment for AEs and laboratory tests will be performed according to NCI CTCAE v4.03. All AEs/SAEs will be recorded in the CRF from the time of signing the ICF to the end of safety follow-up or the start of new anti-tumor therapy (whichever occurs first). The definition, recording, causality assessment, severity assessment, reporting time limit, handling, and follow-up of AE and SAE should refer to the description in Section 9 of the protocol.

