21. 200 mg of SHR-1210, intravenous drip infusion, once every 2 weeks. Subjects who meet specific conditions may continue the medication after PD (refer to Section 6.1.2 of the protocol for continued medication beyond progression).
22. Eligible subjects after screening will be randomized in a 1:1:1 ratio into the following three treatment groups: apatinib 375 mg, PO, QD; apatinib 375 mg, PO, QD (5 Days on, 2 Days off); or apatinib 375 mg, PO, QD (7 Days on, 7 Days off). Apatinib should be administered at a fixed time every day as much as possible. On the day of SHR-1210 infusion, apatinib shall be administered 30 min after the end of SHR-1210 infusion.
23. Subjects are required to provide archived or fresh tumor tissue samples that meet the testing requirements during the screening period. After obtaining the subject's ICF, another biopsy may be performed at the end of treatment. Tumor tissue samples to be provided at screening (required) and the end of treatment shall be 5-10 unstained tissue slices with a thickness of 4-6 μ m, among which at least 5 sections are used for PD-L1 testing.
24. After the subject's ICF is obtained, about 16 mL of peripheral blood may be collected for tumor biomarker detection during the screening period, at each tumor evaluation, and the end of the treatment.
25. Randomization must be completed within 24 h before the first dose of the study drug.
26. End of treatment refers to confirmation of progressive disease or withdrawal from study, and shall be carried out within \pm 3 days when the decision of treatment discontinuation and/or withdrawal from study is made.
27. Safety follow-ups will be performed 90 ± 7 days after the last dose.
28. Survival follow-ups: Performed once every 8 weeks (\pm 7 days) after the last dose, and telephone interviews are acceptable.

ABBREVIATIONS

Abbreviations	Full Name
ADA	Anti-drug antibody
AE	Adverse event
AESI	Adverse event of special interest
AIDS	Acquired Immune Deficiency Syndrome
ALB	Albumin
ALP	Alkaline phosphatase
ALP	Alkaline phosphatase
ALT	Alanine aminotransferase
ANC	Absolute neutrophil count
APTT	Activated partial thromboplastin time
AST	Aspartate transferase
BASO	Basophil cell count
CFDA	China food and drug administration
BUN	Blood urea nitrogen
CK	Creatine kinase
CK-MB	Creatine kinase isoenzyme
CR	Complete response
Cr	Creatinine
CRF	Case report form
CTLA-4	Cytotoxic T lymphocyte-associated antigen-4
DCR	Disease control rate
DLT	Dose-limiting toxicity
DoR	Duration of response

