6.5 Concomitant Medications

The use of drugs or vaccines explicitly prohibited in the exclusion criteria is prohibited during the entire study. If any explicitly prohibited drug or vaccine is clinically indicated during the study, the interruption of study treatment may be required. The investigator shall discuss with the sponsor's medical department. The decision whether the subject continues to participate in the study treatment or vaccination arrangements needs to be jointly decided by the investigator, the sponsor, and the subject. The investigator and/or the subject's attending physician shall make the final decision on supportive therapy or vaccination.

All drugs related to the treatment of AEs other than solvents within 28 days before the first dose of the study drug until 30 days after and 30-60 days after the end of the treatment should be documented in the CRF, including the name, dose, route of administration, frequency of administration, purpose, and start and end dates.

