7.2.3 End of treatment

End of treatment refers to confirmation of progressive disease or withdrawal from the study. The end-of-treatment visit should be performed within ±3 days of the decision of treatment discontinuation and/or withdrawal from the study (refer to Table 13).

Table 13. Procedures of the end-of-treatment visit

Period	End of treatment	Note 28 Days (± 7 Days)
Day	± 3 days	
Vital Signs	X	Vital signs include body temperature, pulse, respiratory rate, and blood pressure. See Section 8.2.4 of the protocol for detailed requirements
Body Weight	X	
Physical Examination	X	See Section 8.2.2 of the protocol
ECOG PS	X	
Laboratory tests		
12-Lead ECG	X	Refer to Section 8.2.3 of the protocol for details
Hematology/Clinical Chemistry/Urinalysis/Routine Stool	X	See Section 8.2.1 of the protocol
Coagulation Function	X	
Pregnancy Test		Serum pregnancy test
Thyroid Function	X	
Myocardial Zymogram	X	
Pituitary Adrenal Axis Test	X	Applicable to hospitals where conditions permit
Echocardiography	X	
Pulmonary function test and arterial blood gases		Performed when clinically indicated per the investigator's judgment
Immunogenicity (ADA, Nab)	X	

Period	End of treatment	Note 28 Days (± 7 Days)
Day	± 3 days	
AE Assessment	X	All AEs from the time of signing the ICF to the end of safety follow-up or the start of new anti-tumor therapy (whichever occurs first) and all SAEs from signing of ICF to the end of safety follow-up will be recorded in the CRF
Concomitant Medications	X	Drugs related to the treatment of AEs other than solvents within 28 days before the first dose of the study drug until 30 days after and 30 to 60 days after the end of the treatment should be documented
Response Evaluation		
Imaging Assessment	X	See Section 8.1 of the protocol
Exploration of Biomarkers		
Archived or Fresh Tumor Tissue Sample	X	5-10 unstained tissue slices with the thickness of 4-6 µm, among which at least 5 slices will be used for PDL1 testing
Peripheral Blood	X	16 mL of peripheral blood will be collected for tumor biomarker detection

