9.1.1 Definition of AE

AE refers to any untoward medical condition in a clinical study subject who receives a pharmaceutical product, and the condition does not necessarily have a causality with the treatment. All AEs from signing of the informed consent form to the end of the safety follow-up period (90 days after the last dose) or the start of other anti-tumor treatments will be collected in this study. AEs can include any unfavorable and unintended symptoms, signs, abnormal laboratory findings, or diseases, including the following:

- 1) Worsening of pre-existing (prior to entering the clinical trial) medical conditions/diseases (including worsening symptoms, signs, or laboratory abnormalities);
- 2) Any new AE: Any new adverse medical conditions (including symptoms, signs, and newly diagnosed diseases);
- 3) Clinically significant abnormal laboratory findings.

All AEs should be documented in detail by the study personnel, including: the name of the AE and description of all relevant symptoms, onset time, severity, causality assessment, duration, measures taken, as well as final results and outcomes.

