5.5.1 Adverse events

Adverse events (AEs) will be analyzed based on the treatment-emergent adverse events (TEAEs):

- 1) All AEs that occur from the first study dose to 90 days after the last dose;
- 2) An AE that starts before the first study dose but worsens after administration.

Treatment-related AEs are defined as TEAEs with a causality of definitely related, possibly related, or indeterminable. If the relationship between an AE and the study drug is missing, the AE will be considered as a treatment-related AE.

All AEs will be coded with MedDRA 21.0. and graded by NCI-CTCAE v4.03. For the same SOC and/or PT, multiple cases of the same events that occur in one subject will be counted only once. For the same AE reported in one subject multiple times but varying in CTCAE grade, the AE of the greatest grade will be enumerated.

The incidence of AEs will be sorted from high to low based on their corresponding SOC in the SHR-1210 200 mg, IV, Q2W + apatinib 375 mg (or apatinib 250 mg), PO, QD group. The incidence of AEs in each SOC will be sorted from high to low based on their PT. If the incidences of \geq 2 PTs are equal, the AEs will be sorted alphabetically. If there is no AE under a SOC or PT, then analysis is not conducted.

The number of TEAE cases as well as the number of subjects based on the SS will be summarized in a table by dose group. The summary table should at least include the number of subjects with at least one TEAE/SAE/, TEAEs leading to treatment discontinuation, TEAEs leading to dose interruption or dose reduction, SAEs, SAEs leading to death, TEAEs of special interest, immune-related TEAEs (irAEs), and CTCAE grading. For all categories included in the summary table, CTCAE Grade ≥ 3 TEAEs and treatment-related AEs with an incidence of $\geq 5\%$ will be summarized by SOC and PT, respectively. Laboratory abnormalities with an incidence of $\geq 10\%$ will be summarized. TEAEs leading to treatment discontinuation, TEAEs leading to dose interruption or dose reduction, and all treatment-related AEs will be analyzed respectively for SHR-1210 and apatinib. An immune-related AE is determined in the case of an indeterminable immune-related AE.

In particular, the incidences and outcomes of AEs assessed per the CTCAE 4.03 below are separately analyzed:

- Hematologic toxicity
 - Grade 4, or
 - Grade ≥ 3 thrombocytopenia with hemorrhage, or
 - Grade ≥ 4 neutropenia with pyrexia and infection

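### Table 14 puts the safety follow-up visit at day 28 while the rest of the plan puts it at day 90, and the recording of AE treatment and the post-treatment ADA samples are not aligned with either visit schedule

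*Protocol*

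**What the plan says.** **Visit timing.** Protocol Section 7.2.4 says "Safety follow-ups will be performed 90 ± 7 days after the last dose" and refers to Table 14 for the procedures. The Table 1 column header and note 27 also give 90 ± 7 days. The Day row of Table 14, in both parts of the table, gives 28 ± 7 days. Table 13 covers the end-of-treatment visit, which is due within 3 days of the decision to stop, but its Note column header carries the same 28-day label.

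**AE window.** Section 9.1.1 closes the safety follow-up period "90 days after the last dose", or at the start of other anti-tumor treatment. SAP 5.5.1 defines TEAEs to include "All AEs that occur from the first study dose to 90 days after the last dose". The recording rule printed in Table 14 ends at the end of safety follow-up and gives no day count of its own.

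**Drugs given for AEs.** Section 6.5 requires these to be documented "until 30 days after and 30-60 days after the end of the treatment". Note 19 to Table 1 and the Note columns of Tables 11 to 14 repeat the limit.

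**ADA sampling.** Note 17 to Table 1 calls for samples "once per month at safety follow-ups after withdrawal for 3 times", if applicable, and Section 8.5 says the same. Table 1 has a single safety follow-up column.

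**The concern.** AE incidence is one of the two primary endpoints (Protocol 3.2.1). Post-treatment AEs are captured at the sites, and Table 14 is the page a site would use to run the visit. If a site reads day 28 as the end of safety follow-up, three things follow:

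- AE recording may stop there while the SAP still counts to day 90.
- The laboratory tests, ECG and vital signs meant for about day 90 would be done about two months early, or not done at day 90.
- The analysis may not reveal the difference. SAP 5.1.5 summarizes post-baseline data by the visit shown in the eCRF, regardless of whether the protocol window was exceeded.

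The limit on recording AE drugs matters for a related reason. One component of the primary safety definition is Grade 3 or higher laboratory abnormalities that lead to intervention, and the SAP's important TEAEs include those given corrective medication. Both draw on treatment information, and the required drug record ends before the AE window does.

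**Working it through.** No sample-size or power figure is involved, so the check compares the windows.

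**1. Visit windows, in days after last dose.**
- Section 7.2.4, Table 1 and note 27: 90 − 7 = 83 to 90 + 7 = 97.
- Table 14: 28 − 7 = 21 to 28 + 7 = 35.
- Gap between the windows: 83 − 35 = 48 days. Nominal difference: 90 − 28 = 62 days.

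No single visit can satisfy both.

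**2. Which statement is the outlier.** Four places give 90 days for the visit or the AE window: 7.2.4, Table 1 with note 27, 9.1.1 and SAP 5.5.1. Only the Table 14 Day row gives 28 days as a visit time. The Table 13 label serves no purpose there, which suggests a leftover header.

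**3. What a day-28 stop could miss.** In calendar terms, 62/90 = 69% of the window lies after day 28. That is not a share of AEs, because the documents give no post-treatment onset pattern. Under assumed patterns, the share of 90-day events with onset by day 28 is:
- uniform onset: 28/90 = 31%;
- exponential decay, (1 − e^(−28λ)) / (1 − e^(−90λ)) with λ = ln 2 / half-life: 74%, 54% and 43% for half-lives of 15, 30 and 60 days.

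A site that stopped at day 28 would therefore miss between 26% and 69% of post-treatment onsets under these assumptions. This applies only to sites that make the error and to subjects whose AE collection would otherwise run the full 90 days.

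**4. Drug records.** On the longer reading of 6.5, recording ends 60 days after end of treatment. If end of treatment falls d days after the last dose, the uncovered part of the AE window is 90 − (60 + d) = 30 − d days. With d = 0 that is 30 of 90 days (33%), and it shrinks as d grows. If the limit is read as 30 days, it is 60 − d. The anchors do differ: 9.1.1 counts from the last dose, while 6.5 counts from end of treatment, which 7.2.3 defines as confirmed progression or withdrawal. Under the onset patterns in step 3, day 60 covers 67% (uniform) and 95%, 86% and 77% (half-lives of 15, 30 and 60 days).

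**5. ADA samples.** Taking a month as 28, 30 or 30.4375 days, the three samples fall at about days 28–30, 56–61 and 84–91. The first falls within 28 ± 7, the third within 90 ± 7, and the second within neither. The series fits a 90-day period, but with one scheduled visit, two of the three samples have no safety visit under either version.

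**The case against.** The case for treating this as minor is good, and much of it stands. Several stronger conclusions that a reader might draw are not supported:

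- **That the primary safety analysis is ambiguous.** It is not. Section 9.1.1 and SAP 5.5.1 both fix 90 days after the last dose.
- **That a site on Table 14 has no contact after day 28.** Survival follow-up is due every 8 weeks ± 7 days after the last dose (7.2.5), so at about day 56, and subjects who stop without radiologically confirmed progression continue imaging where possible (5.4.3). What can be said is that these are not AE visits: Table 1 assigns survival status and subsequent treatment to the survival contacts.
- **That AE treatment after day 60 goes unrecorded.** Section 9.1.1 requires the action taken and the outcome for every AE in the collection period, and 9.2.6 requires similar detail for SAEs. Whether a laboratory abnormality led to intervention can usually be judged from that record. What is not required is the drug's name, dose and dates.
- **That ADA sampling fits no schedule.** Three monthly samples span about 90 days, and the ADA set needs only a baseline and one post-baseline result.
- **That 69% and 33% are shares of lost AEs.** They are calendar shares. Under the 90-day schedule too, there is no safety follow-up visit before day 83, and AE collection may end earlier when new anti-tumor treatment starts.

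The objection does not remove the site-level risk. Table 14 is the operational page, its AE rule depends on when safety follow-up ends, and the only day count on that page is 28.

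**Conclusion.** The contradiction is real and the plan is wrong as written, but the consequence is operational. Two non-overlapping times are given for one visit, and the table that sites are sent to is the outlier. Centers could differ in when they stop recording AEs and whether they do the day-90 assessments, so one of the primary endpoints could be captured unevenly. The amount lost cannot be derived from the documents: it depends on how many sites follow Table 14 and on when post-treatment AEs start, and the 26% to 69% range rests wholly on assumed onset patterns.

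The drug-record gap is narrower. It covers roughly the last month of the AE window if end of treatment and last dose nearly coincide, and it mainly affects support for the SAP category of TEAEs given corrective treatment. The ADA point concerns a secondary endpoint and is a scheduling omission.

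The choice of Stage II regimen, made on Stage I safety data after Cycle 1, does not depend on the follow-up visit. Nor do ORR, the responder rule, sample size, alpha or power. The correction should be made because it is nearly free and protects a primary endpoint.

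**What to change.** Three reconciliations, with the timing left to the sponsor:

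1. Bring the Table 13 and Table 14 headers into agreement with Section 7.2.4, Table 1 with note 27, Section 9.1.1 and SAP 5.5.1, and state in Table 14 the day on which safety follow-up ends.
2. Make the recording window for AE drugs (Section 6.5, note 19 and Tables 11 to 14) consistent with the AE collection window, use one anchor date for both, and replace the two-part 30 and 30–60 day wording with a single limit.
3. Reconcile note 17 and Section 8.5 with the visit schedule, so that each of the three post-treatment ADA samples has a stated time and a visit or contact at which it is drawn.

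The cost is corrections to protocol tables and wording, carried into the eCRF completion guide. The SAP's TEAE definition needs to change only if the sponsor settles on a period other than 90 days. For data already collected, listing the actual day of each safety follow-up visit by center would show whether any site worked to day 28.

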7.2.5 Survival follow-up

Survival follow-ups will be performed once every 8 weeks (\pm 7 days) after the last dose and telephone interviews are acceptable.

7.3 Procedures of Continued Medication After Progressive Disease

See Section 6.1.2 of the protocol for the procedures of continued medication after PD. Refer to [Table 1](#) Schedule of Study Procedures for details.

8 STUDY ASSESSMENT

8.1 Efficacy Evaluation

This study does not involve central imaging review. The primary analysis of this study will be based on the tumor assessment conducted by the study centers per RECIST v1.1 (refer to Appendix 3). The ORR, PFS, TTR, DoR, DCR, 6-month OS rate, and OS after medication are evaluated.

8.1.1 Sites of radiographic scans

The method used for tumor imaging evaluation during the baseline period must be consistent with the method used for each subsequent follow-up evaluation. Computerized tomography (CT) or magnetic resonance imaging (MRI) scans is recommended. Other involved parts are examined

based on the symptoms and signs of each subject. Baseline imaging evaluations should include thoracic, abdominal, and pelvic scans (from apex of lung to pubic symphysis), brain scan, bone scan, and scan of all known or suspected lesions. Each subsequent clinical tumor imaging evaluation should include thoracic, abdominal, and pelvic scans; brain and/or bone scans may be performed when clinically indicated. The frequency of imaging monitoring can be increased by the investigator as needed.

8.1.2 Evaluation time points

The baseline tumor evaluation will be performed within 28 days before the first dose. Imaging data obtained before the signing of informed consent form may be used for tumor evaluation during the screening period as long as it meets the requirements of the protocol.

During the study, imaging assessment will be performed on C1D28 and every 8 weeks (± 7 days) after C1D28 until radiographic PD is documented. An additional imaging evaluation must be performed in 4 weeks (+ 7 days) for confirmation after the initial documentation of response (CR or PR) and imaging PD.

Criteria for relapse of PD:

1. At 2 consecutive visits, the sum of the diameters of the target lesions increased by $\geq 20\%$ from the lowest value (the smallest sum of diameters may occur at baseline or subsequent visits) and the absolute value increased by ≥ 5 mm, and/or
2. At the time point of confirming PD, non-target lesions or new lesions have significantly progressed (exacerbated) relative to the first time point when progression of non-target lesions are discovered or new lesions are discovered (such that if the target lesions appeared CR, PR, or SD, the total tumor burden has increased sufficiently to discontinue treatment), and/or
3. Compared to the first time point when new lesions are discovered, new lesions appeared at the time point of confirming PD.

If PD is not confirmed, the study medication and imaging evaluation are continued until relapse of PD. Refer to Section 6.1.2 of the protocol for the relapse of PD. Subjects with relapse of PD must discontinue treatment. If the treatment is discontinued for reasons other than radiologically confirmed PD, imaging evaluations shall be performed as much as possible per the scheduled time points until any of the following events occurs: start of new anti-tumor therapy, PD, withdrawal of ICF, or death. Refer to Section 7 of the protocol for details.

If the investigator is unable to determine whether the disease is progressing, especially if the determination of non-target lesions and new lesions is uncertain, the subject may continue the treatment, and when clinically indicated or at the next scheduled assessment, the subject will be reassessed for the disease status. If PD is confirmed by scan reexamination, the date of progression should be the date of initial discovery.

The interruption of one or more study drug(s) does not affect the evaluation frequency per RECIST v1.1.

